10.6.8.1.4. Adverse Events of Special Interest

Based on the mechanism of action of etrasimod and prior experience with other agents acting via a similar mechanism, potential adverse events of special interest (AESIs) will be identified. In addition to appropriate reporting of these events as an AE or SAE, supplementary detailed information may be collected.

Potential AESI for etrasimod include but are not limited to:

- Cardiovascular events (eg, bradycardia, AV conduction delay, and hypertension)
- Macular edema
- Pulmonary events (airflow obstruction or altered gas exchange)
- Infections (severe infections, opportunistic infections, Herpes simplex, and Herpes zoster)
- Liver injury
- PRES
- Malignancies

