Study Design: 
This Phase 2, randomized, double-blind, multi-center study will evaluate the efficacy, safety, and pharmacokinetics (PK) of etrasimod compared with placebo in adults with active EoE. The study will consist of a Screening Period of up to 35 days, 24 weeks of double-blind treatment (Double-Blind Treatment Period), 28 weeks of active extended treatment (Extension Treatment Period), and 4 weeks of follow-up (Safety Follow-Up Period) for a total study duration of up to 61 weeks.
 
Eligible subjects will be randomized in a double-blind fashion (3:3:2 ratio) to etrasimod 1 mg, etrasimod 2 mg, or matching placebo once daily. Randomization will be stratified by baseline history of esophageal dilation (yes/no) and concurrent proton pump inhibitor (PPI) therapy (yes/no).
 
All subjects who complete the Double-Blind Treatment Period and meet eligibility criteria for the Extension Treatment Period may enter the Extension Treatment Period. Subjects who were in the etrasimod 1 mg or etrasimod 2 mg groups in the Double-Blind Treatment Period will continue the same etrasimod dose in the Extension Treatment Period. Subjects who were in the placebo group during the Double-Blind Treatment Period will be re-randomized (1:1 ratio) to etrasimod 1 mg or etrasimod 2 mg at entry into the Extension Treatment Period.
 
Subjects will have follow-up visits at 2 and 4 weeks after the last dose of study treatment after Week 52 or the Early Termination (ET) Visit.

Number of Subjects (planned):

Approximately 96 subjects are planned to be enrolled.

Eligibility Criteria for the Double-Blind Treatment Period:

Key Inclusion Criteria (Full Inclusion Criteria Are Provided in the Protocol)

- Men or women between 18 and 65 years of age at the time of informed consent (IC)
- Have an EoE diagnosis prior to screening and histologically active disease with an esophageal peak eosinophil count (PEC) of ≥ 15 eosinophils (eos)/high power field (hpf) (~ 60 eos/mm²) from any level (proximal, mid, or distal) of the esophagus at the Screening esophagogastroduodenoscopy (EGD)
- Have dysphagia, defined as solid food going down slowly or getting stuck in the throat with an average frequency of ≥ 2 episodes per week over 2 weeks (as documented using the Dysphagia Symptom Questionnaire (DSQ) during the Screening period)

Key Exclusion Criteria (Full Exclusion Criteria Are Provided in the Protocol)

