AZA	azacytidine
β-hCG	beta-human chorionic gonadotropin
BP	blood pressure
bpm	beats per minute
CBC	complete blood count
CD	Crohn's disease
CFR	Code of Federal Regulations
cGMP	current Good Manufacturing Practices
CI	confidence interval
CMH	Cochran-Mantel-Haenszel
CMP	Clinical Monitoring Plan
COPD	chronic obstructive pulmonary disease
COVID-19	coronavirus disease 2019
CRA	clinical research associate
CRO	contract research organization
CSR	clinical study report
CTCAE	Common Terminology Criteria for Adverse Events
CYP	cytochrome P450
DLCO	diffusing capacity of the lungs for carbon monoxide
DNA	deoxyribonucleic acid
DSQ	Dysphagia Symptom Questionnaire
ECG	electrocardiogram
eCRF	electronic case report form

Abbreviation	Explanation
eDiary	electronic diary
EEn	eosinophilic enteritis
EG	eosinophilic gastritis
EGD	esophagogastroduodenoscopy
eGFR	estimated glomerular filtration rate
EGID	eosinophilic gastrointestinal disease
EoE	eosinophilic esophagitis
EoE-HSS	Eosinophilic Esophagitis Histology Scoring System
EoE-QOL-A	Adult Eosinophilic Esophagitis Quality of Life
eos	eosinophils
EREFS	Eosinophilic Esophagitis Endoscopic Reference Score
ET	Early Termination
FA	fluorescein angiogram
FAQ	Food Avoidance Question
FCS	fully conditional specification
FDA	Food and Drug Administration
FEV 1	forced expiratory volume at 1 second
FAS	Full Analysis Set
FSH	follicle-stimulating hormone
FVC	forced vital capacity
GCP	Good Clinical Practice
GERD	gastroesophageal reflux disease
GI	gastrointestinal
GWAS	genome-wide association studies
HBsAg	hepatitis B surface antigen
HBV	hepatitis B virus
HCV	hepatitis C virus
HIV	human immunodeficiency virus
hpf	high power field
HR	heart rate
HSS	Histology Scoring System
IAC	independent adjudication committee
IB	Investigator's Brochure

Abbreviation	Explanation
IC	informed consent
ICF	informed consent form
ICH	International Council for Harmonization
IEC	Independent Ethics Committee
IgE	immunoglobulin E
IL	interleukin
IMID	immune-mediated inflammatory disorder
IND	Investigational New Drug
INR	international normalized ratio
IRB	Institutional Review Board
IUD	intrauterine device
IV	intravenous
IWRS	Interactive Web Response System
JAK	Janus kinase
LS	least square
6-MP	6-mercaptopurine
MAR	missing at random
MedDRA	Medical Dictionary for Regulatory Activities
MH	Mantel-Haenszel
mFAS	modified Full Analysis Set
MI	multiple imputation
MMF	mycophenolate mofetil
MTX	methotrexate
NASH	nonalcoholic steatohepatitis
OCT	optical coherence tomography

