18.2.6. TEAEs OF SPECIAL INTEREST

Categories of Targeted Medical Events (TMEs) and a list of preferred terms associated with these TME categories were developed based on the mechanism of action of etrasimod, prior experience with other agents acting via a similar mechanism, and disease-specific clinical judgment. In addition, where standard testing has been implemented to screen for potential AEs (eg, electrocardiograms, spirometry, serum transaminases, etc.), the relevant data will be reviewed to identify potential cases of AESI that investigators may not have identified and to provide quantitative data for AESIs. The proposed candidate terms will be reviewed to identify which events reflect AESI.

TEAEs of special interest will be summarized by category, subcategory, and PT by descending frequency by treatment group. Categories and subcategories of TEAEs of special interest are the following:

- Cardiovascular Events
 - Bradycardia
 - AV conduction delay
 - Hypertension
- Infections
 - Severe infections
 - Opportunistic infections (Narrow)
 - Herpes simplex and herpes zoster
- Macular Edema
- Pulmonary Disorders
 - Airflow obstruction (forced expiratory volume in 1 second [FEV₁], forced vital capacity [FVC])
 - Decrease gas exchange (diffusing capacity of the lungs for carbon monoxide [DLCO])
- Liver Injury
 - Liver transaminases elevation
 - Bilirubin elevation
 - Elevated BP
- Posterior reversible encephalopathy syndrome (PRES)
- Malignancies

For the TEAE of special interest, the Exposure-adjusted incidence rate (EAIR) will also be provided for the following group based on the subject in Safety Set in Double-Blinded Treatment Period

Group 1: Subjects who take etrasimod 2 mg anytime during the course of study. This includes the subjects who

- receive the etrasimod 2 mg in Double-Blind Treatment period and continue receiving Etrasimod 2 mg in Extension Treatment period, or
- receive the etrasimod 2 mg in Double-Blind Treatment period and discontinue early without entering Extension Treatment period, or
- receive the placebo in Double-Blind Treatment period and receive etrasimod 2 mg in Extension Treatment period

Group 2: Subjects who take etrasimod 1 mg anytime during the course of study. This includes the subjects who

- Subjects who take etrasimod 1 mg anytime during the course of study. This includes the subjects who

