- receive the etrasimod 1 mg in Double-Blind Treatment period and continue receiving etrasimod 1 mg in Extension Treatment period, or
- receive the etrasimod 1 mg in Double-Blind Treatment period and discontinue early without entering Extension Treatment period, or
- receive the placebo in Double-Blind Treatment period and receive etrasimod 1 mg in Extension Treatment period

Group 3: Subjects who take placebo in Double-Blind Treatment period

The EAIR for a given TEAE of special interest is calculated as the number of subjects with the TEAE of special interest divided by the total exposure in subject-years. The 95% confidence interval (CI) of the EAIR will be provided along with EAIR. Some notes for the exposure and AE used in EAIR calculation are provided as follows

Group	Note for Exposure used in EAIR calculation	Note for TEAE of special interest used in EAIR calculation
1)	sum of either time (year) from first dose of etrasimod 2 mg to the onset of first such event for those who experienced the TEAE of interest, or time (year) from first dose of etrasimod 2 mg to last participation for those who did not experience the TEAE of special interest.	For a placebo subject who receive 2 mg in Extension Treatment period, only the AE that started or worsened in severity on or after the first dose of etrasimod 2 mg in Extension Treatment period will be included in the EAIR for the subject
2)	sum of either time (year) from first dose of etrasimod 1 mg to the onset of first such event for those who experienced the TEAE of interest, or time (year) from	For a placebo subject who receive 1 mg in Extension Treatment period, only the AE that started or worsened in severity on or

	first dose of etrasimod 1 mg to last participation for those who did not experience the TEAE of special interest.	after the first dose of etrasimod 1 mg in Extension Treatment period will be included in the EAIR for the subject
3)	sum of either time (year) from first dose of placebo to the onset of first such event for those who experienced the TEAE of interest during Double-Blind Treatment period, or time (year) from first dose of placebo to last participation for those who did not experience the TEAE of special interest. during Double-Blind Treatment period	For a placebo subject in Double Blind Treatment period, only the AE that started or worsened in severity on or after the first dose of placebo in Double Blind Treatment period will be included in the EAIR for the subject

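### SAP 18.2.6 lists Elevated BP as a subcategory of the Liver Injury AESI, while the protocol and the SAP's own list place hypertension under cardiovascular events

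*Protocol*

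**What the plan says.** Protocol 10.6.8.1.4 lists potential AESIs for etrasimod. One entry is "Cardiovascular events (eg, bradycardia, AV conduction delay, and hypertension". Liver injury is a separate entry with no blood-pressure component.

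SAP 18.2.6 turns that list into reporting categories and subcategories. Cardiovascular Events has three subcategories, the third being "Hypertension". Liver Injury also has three: raised transaminases, raised bilirubin and Elevated BP. The SAP's list of abbreviations gives BP as "blood pressure".

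The categories govern the output: "TEAEs of special interest will be summarized by category, subcategory, and PT by descending frequency by treatment group". SAP 18.2.6 also provides an exposure-adjusted incidence rate (EAIR) with a 95% confidence interval, "calculated as the number of subjects with the TEAE of special interest divided by the total exposure in subject-years". Before the tables are made there is a review step: "The proposed candidate terms will be reviewed to identify which events reflect AESI". The SAP says that a list of preferred terms was developed for these categories, but neither document reproduces it. SAP 3.3 reports no departure from the protocol's analysis.

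**The concern.** The SAP gives raised blood pressure two homes, and one of them is an organ category to which the protocol does not assign it. Because the subcategory decides the category in which an event is counted, this is an operative rule and not background text. Followed literally, a subject reported with increased blood pressure would be counted under Liver Injury, and a subject reported with hypertension under Cardiovascular Events. The liver row would then contain events that are not hepatic, and the cardiovascular row would miss events that belong to it. Both are AESIs that the protocol names, and with arms of this size one or two misplaced subjects can change how a row reads.

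**Working it through.** The plan states no figure on this point, so there is nothing to reproduce. The check is a comparison of texts, followed by an illustration of size.

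**Step 1: the two lists side by side.**

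| Item | Protocol 10.6.8.1.4 | SAP 18.2.6 |
|---|---|---|
| Bradycardia, AV conduction delay | Cardiovascular | Cardiovascular |
| Hypertension | Cardiovascular | Cardiovascular |
| Transaminases, bilirubin | Not itemised; liver injury is its own entry | Liver Injury |
| Elevated BP | No separate entry | Liver Injury |

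The last row conflicts with the protocol's placement of hypertension, and with the SAP's own. The item stands at subcategory level, directly after bilirubin and before posterior reversible encephalopathy syndrome.

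**Step 2: planned arm sizes.** The protocol synopsis says "Approximately 96 subjects are planned to be enrolled", with 3:3:2 allocation.

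- Each etrasimod arm: 96 × 3/8 = 36
- Placebo: 96 × 2/8 = 24

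**Step 3: effect on incidence.** Let L be the number of subjects with a true liver event and b the number whose only event in the category is raised blood pressure. As written, the Liver Injury incidence is (L + b)/n; without the item it is L/n. All values of L and b are assumed.

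- Each such subject adds 1/36 = 2.8 points in an etrasimod arm, or 1/24 = 4.2 points on placebo.
- With L = 1 and b = 0, 1, 2 or 3 in an arm of 36, the result as written is 2.8%, 5.6%, 8.3% or 11.1%. Without the item it is 2.8% throughout.
- With b = 2 and one further subject coded as hypertension, the cardiovascular blood-pressure row shows 1/36 = 2.8%, where all three together would give 3/36 = 8.3%. This assumes that each preferred term is assigned to one subcategory only.

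**Step 4: effect on an EAIR, if one is computed for the category.** Assume full enrolment, no dropout and no censoring at the event.

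- The 2 mg group has 36 subjects for 52 weeks plus 12 former placebo subjects for 28 weeks: (36 × 52 + 12 × 28) × 7/365.25 = 42.3 subject-years. One extra subject adds 100/42.3 = 2.4 per 100 subject-years. Counting 4 weeks of follow-up as well gives 46.0 subject-years and 2.2. The 1 mg group is the same by design.
- Placebo: 24 × 24 × 7/365.25 = 11.0 subject-years, so one extra subject adds about 9.1 per 100 subject-years.

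**The case against.** The strongest reply is that the printed label does not assign events; the preferred-term list and the review of candidate terms do. If that list already sends blood-pressure terms to Cardiovascular/Hypertension, the effect is zero. This stands, and it is why the consequence can only be stated conditionally. It does not remove the defect. The review is described as deciding which events are AESIs; the SAP does not say that it corrects the category structure.

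Second, the line may be a drafting slip. The SAP has others: ulcerative colitis abbreviations under the estimand table in 2.4, an incomplete protocol date in Section 1, and cross-references in 8.3 and 17.1.6.1 to the wrong section numbers. That is plausible, and a mistyped liver parameter is possible too. Either way the third liver subcategory needs correcting.

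Third, neither signal rests on this row alone. SAP 18.2 tabulates all events by system organ class and preferred term. SAP 18.6 reports blood pressure and its markedly abnormal values. SAP 18.4.1 gives liver laboratory summaries and eDISH plots. The AESI table itself goes down to preferred term, so a misfiled event would be visible. This stands and limits the harm to the category total, which those outputs do not correct.

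Fourth, the rate is defined for "a given" event of special interest only in the sense of the SAP's sentence "The EAIR for a given TEAE of special interest is calculated as the number of subjects with the TEAE of special interest divided by" the exposure; it does not say that one is computed per category. That also stands, so Step 4 applies only if a category-level rate is produced.

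**Conclusion.** Wrong as written, minor. SAP 18.2.6 contradicts protocol 10.6.8.1.4 and its own cardiovascular subcategory, with no declared change. If blood-pressure terms are mapped as the list is printed and such events occur, the Liver Injury count, and any EAIR computed for that category, would be overstated, and blood-pressure events would be divided between two categories. Each subject with only a blood-pressure event would add 2.8 points in an arm of 36. How many such subjects there would be cannot be known from the documents.

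A reader might infer more, and the documents do not support it:

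- **That the liver-injury rate is in fact inflated and the blood-pressure signal in fact lost.** The term list is not available, and the effect may be zero.
- **That this bears directly on the choice of dose.** Selecting a dose on efficacy and safety is a primary objective, but no section ties that choice to an AESI category total, and SAP 18 plans no statistical comparisons of safety data unless otherwise specified.
- **That hypertension is an expected effect.** The protocol offers it only as an example of a potential AESI.

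**What to change.** Before unblinding, correct the one line in SAP 18.2.6:

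- If blood pressure was meant, remove Elevated BP from Liver Injury and map terms for increased blood pressure to Cardiovascular Events/Hypertension, in line with protocol 10.6.8.1.4.
- If a liver parameter was meant, replace the label with the name of that parameter. Deleting the line without a replacement would then drop a liver component, so the intended meaning must be settled first.

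Then confirm that the preferred-term list agrees with the corrected categories, and use that list for both the AESI tables and the EAIR. The cost is one line of text and a check of the term list; no analysis is lost.

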10.6.8.1.5. Severity

The severity of each AE will be assessed at the onset by medically qualified personnel in accordance with the local or regional requirements in participating countries. When recording the outcome of the AE the maximum severity of the AE experienced will also be recorded. The severity of each AE will be graded according to the CTCAE:

Grade 1:	Mild; asymptomatic or mild symptoms; clinical or diagnostic observations only; intervention not indicated.
Grade 2:	Moderate; minimal, local or noninvasive intervention indicated; limiting age-appropriate instrumental activities of daily living (ADL).
Grade 3:	Severe or medically significant but not immediately life-threatening; hospitalization or prolongation of hospitalization indicated; disabling, limiting self-care activities of daily living (ADL) (eg, preparing meals, shopping for groceries or clothes, using the telephone, managing money).
Grade 4:	Life-threatening consequences, urgent intervention indicated.
Grade 5:	Death related to AE.

Additional information on CTCAE grading of AEs is provided in [Appendix 8](#).

10.6.8.1.6. Relationship

The Investigator is obligated to assess the relationship (causal relationship) between the study treatment and each occurrence of each AE. The AE relationship (causal relationship) to study treatment must be characterized as one of the following categories:

Not Related:	The AE does not follow a reasonable temporal sequence from administration of the drug, does not abate upon discontinuation of the drug, does not follow a known or hypothesized cause-effect relationship, and (if applicable) does not reappear when the drug is reintroduced, furthermore, there may exist a clear alternative medical explanation (eg, underlying disease state) or association with study procedure or study conduct.
Unlikely Related:	The temporal association between the AE and the drug is such that the drug is not likely to have any reasonable association with the AE.
Probably Related:	The AE follows a reasonable temporal sequence from administration of the drug and cannot be reasonably explained by the known characteristics of the subject's clinical state, environmental, or toxic factors, or other modes of therapy administered to the subject.
Related:	The AE follows a reasonable temporal sequence from administration of the drug, abates upon discontinuation of the drug, follows a known or hypothesized cause-effect relationship, and (if appropriate) reappears when the drug is reintroduced.

The Investigator will use clinical judgment to determine the relationship (causal relationship). Alternative causes, such as underlying disease(s), concomitant therapy, and other risk factors, as well as the temporal relationship of the event to the study treatment administration should be considered and investigated. The Investigator should consult the IB and the Product Information of marketed products within the drug class, when applicable. For each AE/SAE, the Investigator

must document in the medical notes that he/she has reviewed the AE and has provided an assessment of causality. There may be situations in which an SAE has occurred, and the Investigator has minimal information to include in the initial report to the Sponsor; however, the Investigator should always make an initial assessment of causality for every event before the initial transmission of the SAE to the Sponsor. The Investigator may change his/her opinion of causality based on subsequent receipt of information and send an SAE follow-up report with the updated causality assessment. The causality assessment is one of the criteria used when determining regulatory reporting requirements.

10.6.8.1.7. Eliciting, Recording, and Reporting Adverse Events

10.6.8.1.8. Eliciting Adverse Events

Subjects will be instructed that they may report AEs at any time. An open-ended or nondirected method of questioning should be used at each study visit to elicit the reporting of AEs.

10.6.8.1.9. Recording Adverse Events

The AE reporting period for safety surveillance begins when the subject is initially included in the study (date of first signature of informed consent) and continues up to 30 days after the last study treatment administration. If an AE is not resolved or stabilized by this time, the Sponsor in consultation with the Investigator will decide whether to continue to monitor the AE or closeout the event in the database if no further follow-up is necessary.

Investigators are not obligated to actively seek information on AEs or SAEs after the subject has concluded study participation. Any SAE suspected to be related to the study treatment must be reported whenever it occurs, irrespective of the time elapsed since the last administration.

Investigator and study personnel will record all AEs and SAEs whether received through an unsolicited report by a subject, elicited during subject questioning, discovered during physical examination, laboratory testing, and/or other means by recording them on the eCRF and SAE Report Form, as appropriate. The following information should be recorded on the AE eCRF:

- Description including onset and resolution dates
- Whether it met SAE criteria
- Severity
- Relationship to study treatment or other causality
- Outcome

For SAEs, events occurring secondary to the primary event should be described on the SAE Report Form in the narrative description field.

The following should be considered when recording SAEs:

- Death is an outcome of an event. The event that resulted in the death should be recorded and reported on the SAE Report Form and eCRF.
- For hospitalizations, surgical, or diagnostic procedures, the illness leading to the surgical or diagnostic procedure should be recorded as the SAE, not the procedure itself. The procedure should be captured in the narrative as part of the action taken in response to the illness.

